# **12.1** Measurement of effect

Patients will undergo a baseline CT/MRI assessment and be re-evaluated after two cycles, i.e., 8 weeks of treatment and then every two cycles or eight weeks thereafter. If determined clinically necessary by treating physician, CT/MRI assessment may be performed more frequently. The same imaging modality performed at baseline (CT or MRI) will be repeated at

subsequent imaging. Response and progression will be evaluated in this study using standard Response Evaluation Criteria in Solid Tumors (RECIST) criteria, version 1.1.

Target lesions must have a minimum size of at least one diameter of 10mm for liver, soft tissue lesions, lung, and skin. Pathological nodes must be at least 15mm in the short axis to be considered target lesions. The primary tumor is not considered measurable disease. Recurrent or metastatic lesions within a prior radiation field are acceptable as long as disease has progressed in the radiation field by RECIST 1.1 criteria.

# 12.2 Progression-free survival

The primary endpoint is to evaluate the 6-month progression free survival (PFS); hence patients with evaluable disease by RECIST are eligible for the trial. This is defined as the duration of time from start of treatment to time of progression or death from any cause. Patients who are taken off-study because of drug-related toxicity or other adverse event but who are alive and have stable or responding disease at the time of trial discontinuation will continue to follow per protocol, however, if they start another therapy, they will be considered as failure of therapy at that time and will be removed from protocol.

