# 6.1 CRITERIA FOR SUBJECT ELIGIBILITY

# 6.2 Subject Inclusion Criteria

- Pathologically or cytologically MSKCC confirmed esophagogastric adenocarcinoma.
- Metastatic diseases measurable or evaluable on a CT or MRI scan according to RECIST 1.1 criteria. Locally recurrent disease that is not amenable to potentially curative surgery or radiation therapy is also allowed. Lesions must be ≥10mm in size. Recurrent or metastatic disease within a prior radiation field is acceptable as long as the disease has progressed in the radiation field by RECIST criteria. See Section 12.2 for definition of measurable lesions.
- Patients are allowed to have had a maximum of 1 prior chemotherapy regimen for metastatic disease. Patients are allowed to have a maximum of two prior regimens if they previously received neoadjuvant/adjuvant chemotherapy or chemoradiotherapy for their initial localized disease.
- Patients aged 18 years or older.
- Life expectancy of at least 6 months.
- Karnofsky Performance Status (KPS) performance score ≥ 70%.
- Patients must be able to reliably take and swallow oral medications.
- Patients with prior deep vein thrombosis (DVT) or pulmonary embolism (PE) currently on anticoagulation regimen will be permitted.

Adequate bone marrow, liver, and renal function as assessed by the following:

- Hemoglobin  $\geq$  9.0 g/dL.
- Absolute neutrophil count (ANC) ≥ 1,500/mm^3.
- Platelet count  $\geq$  100,000/mm^3.
- Total bilirubin within normal limits, 0–1 mg/dL.
- AST and ALT< 1.5 times ULN. (For patients with liver involvement: AST and ALT≤ 2.5 ULN).
- International normalized ratio (INR) < 2, prothrombin time (PT) < 20 sec, and partial thromboplastin time (PTT) < 55 sec.

- Creatinine < 1.5 x the ULN or GFR<45 ml/min.

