# 8.1 PRETREATMENT EVALUATION

To be completed within 2 weeks of study entry:

- History and physical exam including vitals, height, weight, performance status.
- Evaluation of concomitant medications and toxicity assessment.
- Serum pregnancy test for women of childbearing potential (WOCP) In addition, all WOCP should be instructed to contact the Investigator immediately if they suspect they might be pregnant at any time during the study participation.
- Laboratory evaluation including a complete blood count, PT/PTT, comprehensive chemistry panel (includes BUN, creatinine, ALT, AST, albumin, glucose, total protein, calcium, bilirubin, bicarbonate, sodium, chloride, potassium, alkaline phosphatase).

To be completed within 4 weeks of study entry:

- Electrocardiogram
- CT scan or MRI documenting all measurable or evaluable disease. All measurable lesions used to define response must be >10mm in size. The primary tumor is excluded. Lesions within prior radiation fields are permitted as long as these lesions have documented progression in size.

To be completed any time prior to starting therapy:

- Histological confirmation of esophagogastric adenocarcinoma prior to study enrollment.
- Available tumor tissue (20 unstained slides or tumor block) will be submitted for future molecular analysis (SEE SECTION 10 "Correlative Studies") but not be required prior to registration. Note: if tissue is depleted, patient will still be eligible after discussion with the PI.

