# 12.0 CRITERIA FOR THERAPEUTIC RESPONSE/OUTCOME ASSESSMENT

All patients who receive at least one week of Nintedanib will be evaluable for toxicity and response. Patients who are unable to complete one week of therapy will not be evaluated for toxicity or response and will be replaced by a new patient.

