# 14.0 BIOSTATISTICS

This is a single institution, open-label, non-randomized, single-arm phase II evaluation. The primary objective of this study is to determine the 6 month progression free survival (PFS) for patients with advanced or recurrent EG cancer treated with Nintedanib 200 mg twice per day. PFS is defined in Section 12.2.

We are using 6 month PFS as the primary endpoint in this study of 2nd line treatment for advanced EG cancer. Previous studies have estimated the 6 months to be 4.5% with placebo, 12% with everolimus and 18% for ramucirumab. Based on this information, a 6 month PFS of 10% or less will be considered unacceptable while 28% or more will be considered promising. Using an exact binomial single stage design we require 32 patients to differentiate between 6-month PFS of 10% and 28% with type I and II error rates of 10% each. If 6 or more patients are alive and progression free at 6 months, the regimen is declared promising. With a total of 32 patients, we also have 89% power to detect an improvement in the response rate from 5% to 20% with a one-sided type I error rate of 10%. We assume an accrual rate of 1-2 patients per month for study duration of 18-35 months.

Secondary endpoints involve an assessment of the overall response rate (complete and partial responses), as determined by RECIST criteria. Toxicities will also be assessed and tabulated. Correlative analyses will be exploratory in nature. We will assess the relationship between FGFR amplification (by FISH) and FGFR overexpression (by IHC) with progression free survival using log-rank test. Fisher's exact test will be employed to assess these relationships with response.

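### Patients without measurable disease can enter and count towards the response rate, so the ORR may be diluted downward and its stated 89% power is not assured

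*Combined protocol and SAP*

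**What the plan says.** Entry (Sections 4.3 and 6.2) is open to patients whose disease is either measurable or merely evaluable; Section 6.2 has "Metastatic diseases measurable or evaluable on a CT or MRI scan according to RECIST 1.1 criteria". Section 12.2 gives the reason. After naming 6-month PFS as the primary endpoint it adds "hence patients with evaluable disease by RECIST are eligible for the trial".

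The response denominator is set in Section 12.0: "All patients who receive at least one week of Nintedanib will be evaluable for toxicity and response". Patients who do not complete a week are replaced. Nothing there requires measurable disease.

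Response itself rests on measurement. Section 12.3 makes the best-response assignment depend on RECIST measurement and confirmation criteria and counts CR and PR. Section 8.1 gives a size rule: "All measurable lesions used to define response must be >10mm in size". Section 12.1 requires 15 mm in the short axis for a target node and treats the primary tumor as not measurable.

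Section 14.0 attaches a hypothesis and a power to ORR: "With a total of 32 patients, we also have 89% power to detect an improvement in the response rate from 5% to 20" per cent, with a "one-sided type I error rate of 10" per cent. It makes no allowance for patients without measurable disease. No section defines a measurable-disease subset for response, limits the number of evaluable-only patients, or says how response is assigned when there are no target lesions.

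**The concern.** The argument for admitting evaluable-only disease works for PFS, because progression or death can be recorded without a target lesion. It does not carry over to ORR. A partial response is a measured change, so a patient with nothing measurable has little route to one yet stays in the denominator.

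The 10 mm entry floor in Section 6.2 narrows this group but does not remove it. A patient whose only metastatic disease is a 12 mm node would meet the floor and still have no target lesion under Section 12.1.

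Two things are at stake. A modest ORR could not be told apart from a case mix with many evaluable-only patients. The power in Section 14.0 also treats all 32 patients as able to respond at the design rate. ORR is the first secondary objective and carries its own stated power, so its denominator should be settled before the data are seen.

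**Working it through.** **Inputs.** From Section 14.0: N = 32, p0 = 0.05, p1 = 0.20, one-sided type I error 10%, stated power 89%. The method is given for the primary endpoint ("Using an exact binomial single stage design we require 32 patients") and is assumed here to apply to ORR as well. The only decision rule given is for PFS ("If 6 or more patients are alive and progression free at 6 months, the regimen is declared promising"), so the ORR cut-off below is inferred.

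**Formula.** With X ~ Binomial(m, p), P(X ≥ r) = 1 − Σ C(m,k) p^k (1−p)^(m−k), summed over k = 0 to r−1.

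**Reproducing the stated figure (m = 32).**

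| Cut-off r | P(X ≥ r) at 5% | P(X ≥ r) at 20% |
|---|---|---|
| 3 | 21.4% | 96.8% |
| 4 | 7.4% | 90.7% |
| 5 | 2.0% | 79.6% |

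The smallest cut-off that keeps the type I error at or below 10% is 4. At p = 0.20 the terms for k = 0 to 3 are 0.0008, 0.0063, 0.0246 and 0.0614. They sum to 0.0931, so power is 1 − 0.0931 = 0.907, within 2 points of the stated 89%. The stated figure is therefore reproduced when all 32 patients can respond.

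**Effect of evaluable-only patients.** Let m of the 32 have measurable disease and assume that the rest cannot respond. The denominator stays at 32 and the cut-off at 4. The apparent ORR is 0.20 × m/32, power is P(X ≥ 4) with p = 0.20, and type I error is P(X ≥ 4) with p = 0.05.

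| Evaluable-only | m | Apparent ORR when the true rate in measurable patients is 20% | Type I error | Power |
|---|---|---|---|---|
| 0 | 32 | 20.0% | 7.4% | 90.7% |
| 1 | 31 | 19.4% | 6.7% | 89.3% |
| 2 | 30 | 18.8% | 6.1% | 87.7% |
| 4 | 28 | 17.5% | 4.9% | 84.0% |
| 6 | 26 | 16.3% | 3.9% | 79.3% |
| 8 | 24 | 15.0% | 3.0% | 73.6% |

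The documents do not give the number of evaluable-only patients, so the rows are a range and not a prediction.

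**Relaxing the zero-response assumption.** Suppose 20% of patients are evaluable-only and, for illustration, 5% of those reach a CR. The overall rate is 0.8 × 0.20 + 0.2 × 0.05 = 0.17, and P(X ≥ 4) with m = 32 is 81.7%. With no CRs among them the rate is 0.16 and power is 77.6%. The table above is thus an upper bound on the loss.

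**Effect of restricting the denominator.** The exact cut-off for m measurable patients stays at 4 from m = 32 down to m = 23. The test is then the same with either denominator: 84.0% power at m = 28 and 73.6% at m = 24. Only at m = 22 does the cut-off fall to 3 (type I error 9.5%, power 84.6%). Restriction corrects the estimate; down to 23 measurable patients it recovers no power.

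**The case against.** The strongest defence is that counting all evaluable patients is a legitimate and conservative choice. Patients who cannot respond can only lower the chance of a false positive (4.9% with four of them, against 7.4% with none). ORR is secondary, the protocol openly explains why evaluable disease is allowed, and the PFS decision rule is untouched. All of this stands, and it makes the point minor.

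Three stronger readings are tempting, and the documents do not support them.

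- *The stated power is not delivered.* That depends on a count the documents do not give. With none or one such patient the 89% is met; it is missed from two onward, and then only under the zero-response assumption.
- *Patients without measurable lesions cannot be responders.* No section says so. Section 12.3 counts CR, which remains possible without target lesions, and the sentence in Section 8.1 sets a size for measurable lesions without saying that they alone define response.
- *The observed ORR would not be comparable with the 5% and 20% reference rates.* Section 14.0 gives no source or population for those rates, so nothing shows that they come from patients with measurable disease only.

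It is also fair to object that changing the denominator restores no power over the range tabulated. The case for the change rests on the estimate and on an honest power statement.

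**Conclusion.** The eligibility rule, the response denominator and the measurement-based definition of response do not fit together, and the ORR power takes all 32 patients as able to respond at the design rate. If evaluable-only patients enrol, the ORR may be diluted downward and the 89% is not assured. In the worst case, six such patients would make a true 20% appear as 16.3% and cut power to 79.3%; eight would give 15.0% and 73.6%.

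These sizes rest on three assumptions: an assumed number of evaluable-only patients, no responses among them, and an inferred cut-off of 4 under an exact binomial test. The bias is conservative for type I error and the primary 6-month PFS design is unaffected. This is an inexpensive clarification of a secondary endpoint and does not challenge the trial's main conclusion.

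**What to change.** - **Section 12.0:** separate the two populations. Keep the one-week rule for toxicity, and for response require in addition measurable disease at baseline. If this section is left as it stands, it will contradict the other two changes.
- **Section 12.3:** define ORR in treated patients with measurable disease at baseline. Report the all-treated ORR alongside, and say how response is assigned in patients without target lesions.
- **Section 14.0:** state the ORR cut-off, apply the test to the measurable-disease population, and give the power as conditional on the number measurable (for example 90.7% with 32, 84.0% with 28 and 73.6% with 24).

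The cost is wording only. Section 8.1 already requires the baseline scan to document measurable and evaluable disease, and eligibility, treatment and enrolment do not change. The downside is a lower, conditional power figure. Having 32 measurable patients would mean enrolling about 36 if 10% are evaluable-only (32/0.9) or 40 if 20% are (32/0.8); for a secondary endpoint, stating the conditional power is enough.

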# 12.3 Evaluation of objective response rate

The secondary endpoints include objective response rate, safety and tolerability. The objective response rate will be the best overall response, or the best response recorded from the start of treatment until disease progression/recurrence. The patient's best response assignment will depend on the achievement of both measurement and confirmation criteria by RECIST and defined as complete response (CR), and partial response (PR).

The type, frequency, severity, timing, and relationship of each adverse event will be determined as per the NCI Common Toxicity Criteria, version 3.0. Given the small sample size, the analysis of correlative biomarkers will be exploratory and hypothesis generating.

# 13.1 CRITERIA FOR REMOVAL FROM STUDY

If at any time, the patient develops progressive disease he/she will be taken off study and referred for alternative therapy. If at any time the patient develops unacceptable toxicity that fails to resolve after a maximum treatment delay of 4 weeks, he/she will be removed from study. Before being removed from the study, patients will be scanned to assess the response. If the off study scan shows progression of disease then the patient will be considered as a non-responder, while a CR or PR will be considered as response. A patient will be withdrawn from the study treatment in the following circumstances:

- Patient is no longer able to participate in the study (e.g. AE, surgery, concomitant diagnoses, concomitant therapies or administrative reasons); in such a case the Investigator's reason for patient's removal must be recorded in CRDB.
- Patient withdrawal of consents or election to discontinue participation in the trial.

- Significant deviation from the protocol or eligibility criteria; such patients will be considered protocol violations and removed from study.
- Non-compliance with study or follow-up procedures.
- Drug related AE(s) that have not resolved after 3 weeks of treatment interruption. Exception to this in patients who derive obvious clinical benefit according to the investigator's judgment could be considered upon discussion with Principal Investigator. The dose reduction scheme provided should be followed in this case.
- Repeat episodes of drug related toxicity despite dose reduction to Nintedanib 100mg twice daily dose.
- Documented progressive disease.
- Patients who become pregnant while on study.

As soon as a patient is withdrawn from the study treatment, the End of Treatment (EOT) visit has to be performed (not in case patient has withdrawn consent). Every effort should be made to follow-up patients in case an adverse event is still ongoing at the time of withdrawal.

# 14.0 BIOSTATISTICS

This is a single institution, open-label, non-randomized, single-arm phase II evaluation. The primary objective of this study is to determine the 6 month progression free survival (PFS) for patients with advanced or recurrent EG cancer treated with Nintedanib 200 mg twice per day. PFS is defined in Section 12.2.

We are using 6 month PFS as the primary endpoint in this study of 2nd line treatment for advanced EG cancer. Previous studies have estimated the 6 months to be 4.5% with placebo, 12% with everolimus and 18% for ramucirumab. Based on this information, a 6 month PFS of 10% or less will be considered unacceptable while 28% or more will be considered promising. Using an exact binomial single stage design we require 32 patients to differentiate between 6-month PFS of 10% and 28% with type I and II error rates of 10% each. If 6 or more patients are alive and progression free at 6 months, the regimen is declared promising. With a total of 32 patients, we also have 89% power to detect an improvement in the response rate from 5% to 20% with a one-sided type I error rate of 10%. We assume an accrual rate of 1-2 patients per month for study duration of 18-35 months.

Secondary endpoints involve an assessment of the overall response rate (complete and partial responses), as determined by RECIST criteria. Toxicities will also be assessed and tabulated. Correlative analyses will be exploratory in nature. We will assess the relationship between FGFR amplification (by FISH) and FGFR overexpression (by IHC) with progression free survival using log-rank test. Fisher's exact test will be employed to assess these relationships with response.

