# 3.7 FGFR2 in gastric cancer

The family of fibroblast growth factors (FGFs) and FGF receptors (FGFRs) plays a critical role in cell behaviors, such as proliferation, differentiation, migration and survival, and are fundamental to embryonic development, regulation of angiogenesis, and skeletal development. The FGFR ligands belong to the FGF family comprising of 18 secreted ligands-induced dimerization and bind to adapter proteins. Subsequent downstream signaling occurs through two main pathways via the intracellular receptor substrates FGFR substrate 2 and phospholipase C $\gamma$  (PLC $\gamma$ ), leading ultimately to upregulation of the Ras-dependent mitogen-activated protein kinase (MAPK) and Ras-independent phosphoinositide 3-kinase (PI3K)-Akt signaling pathways).

Activation of FGFRs as a result of amplification, mutation or translocation of FGFR genes or over-expression of FGFR proteins or overproduction of FGF ligands has been shown to be oncogenic. Inhibition of FGFR11may have clinical utility in cancers that overexpress FGFRs, such as breast, esophageal, bladder, gastric, and lung cancers, or display a prevalence of FGFR mutations, such as inbladder cancer.

FGFR gene amplification often leads to FGFR overexpression, which can provoke ligandindependent signaling. FGFR2 amplifications have been reported in up to 7% of gastric cancers, most of which are diffuse-type with relatively poor prognosis. The presence of FGFR2 gene amplifications in gastric cancer is associated with sensitivity to inhibition of FGFR signaling by tyrosine kinase inhibitors and monoclonal antibodies in preclinical models. The frequency of FGFR1 and FGFR2 overexpression is significantly larger than the frequency of amplification in gastric cancers, which is reported up to 41%, indicating that gene amplification is not the sole mechanism leading to receptor overexpression. FGFR2 and PDGFR expression in esophageal and gastric cancers have also been shown to

be associated with high metastatic potential, aggressive tumor biology, and poor outcomes.  $^{\scriptscriptstyle 31,39}$ 

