#### 4.3 Intervention

32 patients will be enrolled on this clinical trial. Patients will receive Nintedanib 200mg twice daily continuously until disease progression, unacceptable toxicity, or serious intercurrent illness develops, or if patient consent is withdrawn.

Patients must have measurable or evaluable disease and undergo a computerized tomography (CT) or magnetic resonance imaging (MRI) scan of their chest and abdomen within 28 days of study enrollment, then at eight weeks, and every eight weeks thereafter (every 2 cycles). For the followup scans, a scheduling window of up to one to fourteen (1-14) days will be permitted. If a complete response is achieve and maintained for 12 months, patients with complete response will then be required to repeat CT or MRI evaluation every 4 months up to 5 years post complete response status, then every 6 months thereafter, with a scheduling window of one to fourteen (1-14) days. Response assessment will be by RECIST 1.1 criteria. The same imaging modality performed at baseline (CT or MRI) will be repeated at subsequent imaging.

Therapy will be administered in the outpatient setting, with each cycle consisting of 28 days of continuous therapy. The cycle start date will coincide with the physician visit date. A study diary will be completed by patients to ensure compliance with the study drug (Appendix I).

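### If FGFR amplification is as rare as the protocol's only quoted rate, the ordinary log-rank p-value for PFS by amplification is unreliable; a minor point, since the analysis is exploratory

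*Combined protocol and SAP*

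**What the plan says.** Section 14.0 plans to relate FGFR amplification and FGFR overexpression to PFS "with progression free survival using log-rank test". For response it chooses an exact method: "Fisher's exact test will be employed to assess these relationships with response". It gives no significance level, sidedness, expected group sizes, minimum group size or exact version for the log-rank test.

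The inputs for the likely group sizes are elsewhere:
- Section 4.3: "32 patients will be enrolled on this clinical trial".
- Section 3.7: "FGFR2 amplifications have been reported in up to 7% of gastric cancers". For overexpression the frequency there is one "which is reported up to 41" per cent.
- Section 8.1 does not make tissue a condition of entry: "if tissue is depleted, patient will still be eligible after discussion". The number with a result may therefore be below 32.

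The plan also limits the weight of this work. Section 14.0 says "Correlative analyses will be exploratory in nature", and Section 12.3 says "Given the small sample size, the analysis of correlative biomarkers will be exploratory and hypothesis generating".

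**The concern.** The usual log-rank p-value treats the standardised statistic as normal. That works when both groups contribute a reasonable number of events. It does not work when one group has one to four patients, because the statistic is then strongly skewed. An amplified patient who progresses early contributes a large observed-minus-expected difference over a very small variance. An amplified patient who progresses late accumulates expected events only slowly.

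The error is therefore directional. Chance findings mostly say that amplified patients do worse. The rationale in Section 3.7 points the other way, towards benefit from FGFR inhibition. The same section also links amplified tumours to poorer prognosis, so a chance adverse result would look believable. At stake is the reading of a secondary, exploratory objective, not the verdict on the drug.

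**Working it through.** **Plan's own figures.** The documents state no size or power for this test, so there is nothing to reproduce for it directly. The primary rule (6 or more of 32, 10% against 28%) has exact binomial type I error 9.4% and power 91.9%, which meets the stated 10% limits. N = 32 is sound for its own purpose.

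**Expected number amplified.** 32 × 0.07 = 2.24. With the count binomial(32, 0.07), P(0) = 9.8%, P(1) = 23.6%, P(2) = 27.6%, P(3) = 20.7% and P(4) = 11.3%. These sum to 93.0%, the chance of fewer than 5. At an assumed 5% prevalence the mean is 1.6.

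**Actual size of the log-rank test.** Assume 32 events, no ties, no censoring and nominal two-sided 5%. With no true effect, every set of rank positions for the m amplified patients is equally likely, so the size can be counted exactly. At each event time, with r₁ amplified among r at risk, add r₁/r to E and (r₁/r)(1 − r₁/r) to V. Then z = (O − E)/√V, compared with ±1.96.

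- *m = 1.* Fifth to progress: E = 0.167, V = 0.161, z = 2.07. Sixth: z = 1.79. Last of 32: E = 4.058, V = 2.444, z = −1.956. Rejections: 5/32 = 15.6%, all in the worse direction.
- *m = 2.* There are C(32,2) = 496 pairs of positions. The worse direction rejects for 48. If the first amplified patient is 1st to progress, the second must be no later than 13th (z = 2.02 at 13th, 1.86 at 14th). Over first positions 1 to 7 the counts are 12 + 10 + 9 + 7 + 5 + 3 + 2 = 48. The better direction rejects for 5 pairs: one patient last and the other 27th to 31st. Size = 53/496 = 10.7%, split 48/496 = 9.7% worse and 5/496 = 1.0% better.

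| Amplified (of 32) | Actual size at nominal 5% | Worse | Better |
|---|---|---|---|
| 1 | 15.6% | 15.6% | 0% |
| 2 | 10.7% | 9.7% | 1.0% |
| 3 | 8.9% | 7.6% | 1.4% |
| 4 | 8.0% | 6.4% | 1.6% |

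**Sensitivity, 2 amplified.**
- Nominal two-sided 10%: 16.1% (13.3% worse, 2.8% better).
- 20, 25 or 28 evaluable patients: 10.3% to 10.6%.
- Censoring at 6 months or at random (simulated): 9.7% to 10.8%.
- 8-weekly scans with dates spread over ±7 or ±14 days (simulated): 9.9% to 11.1%.
- All progressions on identical scan days: 2.2% to 7.5%. With 10% to 25% of events off schedule and no window: 5.7% to 8.6%.

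**Overexpression.** 0.41 × 32 ≈ 13, so about 13 against 19. The size is 5.7% to 5.8%, near nominal.

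**After the change, 2 against 30.** An exact permutation log-rank with p equal to twice the smaller one-sided value has size 4.8%, split 2.4% and 2.4%. Ordering permutations on |z| also gives 4.8%, but split 4.6% worse and 0.2% better, so the two-sided definition matters. With one amplified patient the smallest doubled p-value is 2 × 1/32 = 0.0625, so neither direction can reach 5%. Power stays low. By Schoenfeld's formula, √(32 × 2/32 × 30/32) × ln 2 = 0.949 for a hazard ratio of 0.5, and Φ(0.949 − 1.96) is about 16%. For a hazard ratio of 0.33 it is about 33%.

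**The case against.** The best defence is that the protocol already disclaims these p-values. Section 12.3 gives small sample size as the reason for calling the biomarker work hypothesis generating, and no decision rule depends on the test. That stands, and it keeps the point minor. It does not make a skewed p-value valid, and Section 14.0 already uses an exact test for the same markers against response.

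A reader might also infer more than the documents support:
- *That the test has twice its nominal error, as a fact of the plan.* No level is stated, so 5% is assumed. At 10% the ratio is 1.6 (16.1% against 10%). The excess also depends on event dates that are not heavily tied. The protocol's scan windows make some spread likely, but dating progressions to nominal scan days would remove much of it.
- *That at most about 2 patients can be amplified.* The 7% is FGFR2 in gastric cancer. The planned grouping is FGFR amplification in general, and Section 7.0 also recruits esophageal and gastroesophageal junction tumours. The count could be higher, and 2.24 is an expectation, not a ceiling.
- *That a lone amplified patient can never show benefit.* With 32 patients the most favourable result is z = −1.956, p = 0.0504, a miss by 0.0004. With 33 patients or at a 10% level it would count as significant.
- *That the test could overturn the FGFR hypothesis.* The plan gives it no such role.

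**Conclusion.** The point holds as a minor one. If amplification is near the only rate the protocol quotes, the planned asymptotic log-rank p-value for PFS by amplification is unreliable. Its errors lean heavily towards finding amplified patients worse off: 48 of the 53 false rejections, about 91%, with 2 against 30. The conclusion rests on four assumptions: a two-sided 5% level, a prevalence near 7% or lower, biomarker results for most of the 32 patients, and event dates that are not concentrated on identical scan days. With 3 or 4 amplified patients the inflation is 1.6 to 1.8 times nominal. The overexpression comparison and the primary 6-of-32 conclusion are not affected.

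**What to change.** Amend Section 14.0 for the comparison of PFS by FGFR amplification only:

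1. Replace the asymptotic log-rank p-value with an exact permutation log-rank p-value, defined as twice the smaller one-sided value (capped at 1).
2. When only a handful of patients are amplified, do no test. Fewer than 5 is a reasonable threshold, but it is a judgement. Instead, report each amplified patient's PFS and best response beside the whole-group Kaplan-Meier curve, and give the amplification frequency among tested patients with an exact 95% interval.

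The overexpression log-rank can stay as it is.

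The cost is one or two sentences and a few lines of code. Enrolment, treatment and the primary analysis do not change. The downside is that the amplification comparison will probably be descriptive only: at 7% prevalence the chance of fewer than 5 amplified patients is about 93%. Where the exact test is used it corrects the error rate, but with so few amplified patients it will have little power.
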